2 STUDY OBJECTIVES

The objectives of the study are as follows:

2.1 Primary Objective

To evaluate the safety and tolerability of repeat doses of DCR AUD administered to adult HVs

2.2 Secondary Objective

- To characterize the PD symptom profile of repeat doses of DCR-AUD in adult HVs
- To characterize the plasma PD of repeat doses of DCR-AUD
- To characterize the PK of repeat doses of DCR-AUD in adult HVs

2.3 Exploratory Objective(s)

To explore change in alcohol consumption following treatment with DCR-AUD in adult HVs.

[figure not shown]
3 INVESTIGATIONAL PLAN

3.1 Overall Study Design and Plan

This is a double-blind, randomized, placebo-controlled study of DCR-AUD to evaluate the safety, tolerability, PK, and PD of repeat doses of DCR-AUD in adult HVs.

Participants will receive 3 injections of study intervention (Day 1, Day 29, and Day 57), and have assessment visits through Week 24. Up to 10 EIAs will be conducted over the 24-week period to characterize the PD of DCR-AUD. For each EIA, participants will consume 4 standard drinks over the course of 80 minutes. Participants will be admitted to the clinic overnight for each EIA. At the discretion of the Investigator, participants who present with increasing positive ethanol reaction symptoms at the Day 169 EIA (flushing, headache, lightheadedness, palpitations, nausea, or vomiting) will be followed for an additional 4 weeks (through Day 197).

Figure 3-1 Study Schematic for DCR AUD-102

- a. DCR-AUD (480 mg) or placebo administered on Days 1, 29, and 57
- b. 4-Week conditional follow-up (CFU) conducted at the discretion of the Investigator in participants experiencing symptoms at the End-of-Study (Week 24) visit.

3.2 Endpoints and Associated Variables

The endpoints and variables are provided below.

3.2.1 Primary Endpoints

- Incidence and severity of AEs and SAEs
- Changes from baseline in vital signs, 12-lead ECG, clinical laboratory tests, and physical examination findings.

3.2.2 Secondary Endpoints

- Change in the occurrence and/or severity of 6 symptoms related to plasma acetaldehyde accumulation observed during in-clinic EIAs over the course of the study
- Change in plasma PD biomarker assessments during serial EIA
 - acetaldehyde
 - acetate
 - ethanol
- Plasma PK parameters of DCR-AUD

3.2.3 Exploratory Endpoints

- Change in alcohol consumption from baseline using Timeline Follow Back (TLFB)
- Change from baseline in phosphatidylethanol (PEth) levels, reflecting cumulative recent alcohol ingestion.

3.2.4 Safety Variables

- Physical examinations
- Vital signs (Temperature (by skin refraction), pulse rate, respiratory rate, and blood pressure)
- 12-lead electrocardiograms (ECG): Heart rate, PR interval, QRS interval, QT interval and QT interval using Fridericia's correction [QTcF]
- Columbia-Suicide Severity Rating Scale
- Mini-International Neuropsychiatric Interview.
- Clinical laboratory tests (hematology, clinical chemistry, coagulation and routine urinalysis parameters)
- Adverse event (AE) assessments
- Suicidal Ideation and Behavior Risk Monitoring

3.2.5 Pharmacodynamic Variables

DCR-AUD is designed to selectively reduce ALDH2 activity in the liver and the conversion of acetaldehyde to acetic acid after alcohol consumption. The build-up of acetaldehyde causes unpleasant effects after drinking (e.g., flushing, headache, lightheadedness, palpitations, nausea, or

vomiting). As such, the PD activity of DCR-AUD will be assessed during EIAs via these 6 symptoms, and blood biomarkers (ethanol, acetaldehyde, and acetate) PD parameters to be estimated by Clinical Pharmacology, Modeling and Simulation (CPMS) group are provided in [Table 3-1](#).

Table 3-1 Plasma Pharmacodynamic Parameters

Protocol Parameter	WNL Name	Definition
t_{max}	Tmax	Time corresponding to occurrence of C_{max} (For acetaldehyde, acetate, and alcohol)
C_{max}	Cmax	Maximum observed concentration (in the unit of μM and ng/mL) (For acetaldehyde, acetate, and alcohol)
$C_{maxAbove}$	Cmax_Above_B	Maximum observed concentration that is above the baseline (in the unit of μM and ng/mL) (For acetaldehyde)
baseline	Baseline	Response value just prior to treatment administration
AUC_{Above}	AUC_Above_B	Area under the curve that is above the baseline (for acetaldehyde)
AUC_{Below}	AUC_Below_B	Area under the curve that is below the baseline (for acetate)
AUC_{0-4h}	AUCT	Observed partial area under the curve from time 0 to 4 hours (for acetaldehyde, acetate, and alcohol)
C_{av}	Cav	Average plasma concentration from time zero to 4 hours
PD response change	PD_response_change	Changes in each biomarker level on each EIA day (i.e., D1,14,29,42, 57) compared to the basal level on Day -1
PD response % change	PD_response_%_change	Percent changes in each biomarker level on each EIA day (i.e., D1,14,29,42,57) compared to the basal level on Day -1

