1.1.1. Rationale

DCR-AUD is being developed for the treatment of alcohol use disorder (AUD) in adults using an RNA interference (RNAi) technology platform. DCR-A1203, the drug substance of DCR-AUD, is a synthetic double-stranded (annealed duplex) RNA oligonucleotide conjugated to GalNAc ligands that enable subcutaneous delivery of stable, highly specific, and long-acting knockdown of mRNA in the liver via hepatic GalNAc carbohydrate receptors. The target of DCR-AUD is aldehyde dehydrogenase 2 (ALDH2), one of the primary enzymes required for alcohol metabolism. Alcohol metabolism occurs predominantly in the liver via a 2-step process in which alcohol is first converted to acetaldehyde via alcohol dehydrogenase and then to acetic acid by ALDH2. ALDH2 enzyme inhibition can result in unpleasant symptoms after alcohol consumption such as flushing, headache, lightheadedness, palpitations, nausea, and vomiting, as a result of unmetabolized acetaldehyde accumulation. Unpleasant reactions to alcohol consumption in humans with naturally occurring *ALDH2* mutations are thought to be protective against AUD and account for its low prevalence in individuals who are heterozygous or homozygous for *ALDH2* allele mutations causing slower metabolism of acetaldehyde. The magnitude and duration of acetaldehyde accumulation is proportional to both the degree of ALDH2 enzyme inhibition (e.g., partial vs total) and the amount of alcohol consumed.

DCR-AUD is designed to selectively reduce *ALDH2* mRNA and ALDH2 activity in the liver, and thereby decrease the conversion of acetaldehyde to acetic acid after ethanol ingestion. In cynomolgus monkeys, a single SC dose of 3 mg/kg DCR-AUD resulted in reduction of *ALDH2* mRNA expression in liver up to 112 days postdose, with maximum reduction observed at 4 weeks postdose.

This repeat-dose study is being conducted to characterize the safety and tolerability and PK profiles of DCR-AUD when administered monthly, and to determine if a PD effect (resulting from cumulative *ALDH2* mRNA knock down) can be observed during Ethanol Interaction Assessments (EIA) in a population of social drinkers after repeat doses of DCR-AUD.

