2. INTRODUCTION

2.1. Study Rationale

DCR-AUD is being developed for the treatment of AUD in adults using an RNAi technology platform. DCR-A1203, the drug substance of DCR-AUD, is a synthetic double-stranded (annealed duplex) RNA oligonucleotide conjugated to GalNAc ligands that enable specific hepatic access and uptake after subcutaneous (SC) administration. Once inside the hepatocyte, the antisense sequence of DCR-AUD is designed to target and reduce the expression of ALDH2 mRNA in the liver.

The target of DCR-AUD is ALDH2, one of the primary enzymes required for alcohol metabolism. Alcohol metabolism occurs predominantly in the liver via a 2-step process in which alcohol is first converted to acetaldehyde via alcohol dehydrogenase and then to acetic acid by ALDH2. DCR-AUD is designed to selectively reduce *ALDH2* mRNA and ALDH2 activity in the liver, and thereby decrease the conversion of acetaldehyde to acetic acid after ethanol ingestion. ALDH2 enzyme inhibition can result in unpleasant symptoms after alcohol consumption such as flushing, headache, lightheadedness, palpitations, nausea, and vomiting as a result of unmetabolized acetaldehyde accumulation. Unpleasant reactions to alcohol consumption in humans with naturally occurring *ALDH2* mutations are thought to be protective against AUD and account for its low prevalence in individuals who are heterozygous or homozygous for *ALDH2* allele mutations. The magnitude and duration of acetaldehyde accumulation is proportional to both the degree of ALDH2 enzyme inhibition (e.g., partial vs total) and the amount of alcohol consumed.

Interim results of the ongoing [Study DCR-AUD-101](#), which was the first study of DCR-AUD in humans, have shown DCR-AUD to be safe and well tolerated at doses ranging from 80 to 960 mg, but no PD effects (sufficient elevation of plasma acetaldehyde levels or clinical symptoms) have been observed.

The aims of this repeat-dose study are to characterize the safety and tolerability and PK profiles of DCR-AUD when administered monthly, and to determine if a PD effect (resulting from cumulative *ALDH2* mRNA knock down) can be observed during EIAs in a population of social drinkers after repeat doses of DCR-AUD.

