4.2.4 Baseline

Baseline is defined as the last non-missing measurement prior to the date and time of the dose of study intervention.

For the exploratory analysis using TLFB, baseline is the mean alcohol level as measured on Day -1.

No imputation will be done for missing baseline value for derivation of change from baseline or summary tables and shift tables.

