Individual participant's biomarker (acetaldehyde, acetate, and ethanol) plasma concentration values (baseline unadjusted values only) will be provided by [REDACTED] Laboratories and [REDACTED]. Baseline unadjusted and adjusted acetaldehyde, acetate, and ethanol concentration values will be listed by study day, timepoint, ALDH2 mutation, and participant for the PP by [REDACTED]. Concentration listings will include nominal biomarker sampling time, actual sampling times relative to dose administration, and percentage change from baseline. The corresponding baseline for each timepoint will be taken on Day -1. For the biomarker concentration summary tables, descriptive statistics (N, n, arithmetic

mean, SD, CV%, geometric mean, gCV%, median, IQR (inter quartile range), minimum, and maximum values) will be presented by study day, nominal timepoint, EIA days, and ALDH2 mutation. For time variables only median, T_{min} and T_{max} will be presented. A by participant listing of ALDH2 mutation will be provided.

To visualize the comparison between study days the descriptive biomarker graphs will be generated.

- Figure x.x.x: Individual Participant Profiles for acetaldehyde, acetate, and ethanol, Plasma Concentration Time Data (Unadjusted and Adjusted for Baseline) by study day and EIA day (SP)
- Figure x.x.x: Overlaid Individual Participant Profiles for acetaldehyde, acetate, and ethanol Plasma Concentration Time Data (Unadjusted and Adjusted for Baseline) by study day and EIA day (SP). The profiles for ALDH2 mutation will be plotted with dotted lines.
- Figure x.x.x: Mean (\pm SD) baseline adjusted acetaldehyde, acetate, and ethanol Plasma Concentration Time Data by study day and EIA day (PP)
- Figure x.x.x: Mean (\pm SD) baseline adjusted acetaldehyde, acetate, and ethanol Plasma Concentration without ALDH2 Mutant Time Data by study day and EIA day (PP)
- Figure x.x.x: The Mean (\pm SD) baseline unadjusted acetaldehyde, acetate, and ethanol Plasma Concentration Time profiles by study day and EIA days (PP)
- Figure x.x.x: The Mean (\pm SD) baseline unadjusted acetaldehyde, acetate, and ethanol Plasma Concentration without ALDH2 Mutant Time profiles by study day and EIA days (PP)

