4.12.5 Pharmacodynamic Parameters

DCR-AUD is designed to selectively reduce ALDH2 levels in the liver and the conversion of acetaldehyde to acetic acid. The build-up of acetaldehyde causes unpleasant effects after drinking (e.g., headache, facial flushing, tachycardia, nausea, vomiting). As such, the PD activity of DCR AUD will be assessed during EIAs using blood biomarkers (alcohol, acetaldehyde, and acetate), assessment of 6 symptoms and their severity induced during EIAs, and objective physiological biomarkers (heart rate and facial skin temperature). Participants' subjective experience of the effects

of alcohol will be assessed. Instructions for the collection and handling of biological samples will be provided by the Sponsor in the Laboratory Manual and the Laboratory Specification document.

PD parameters will be calculated using drug effect model from the biomarker time data using Phoenix® WinNonlin® 8.3 or higher. The biomarker parameters alcohol, acetaldehyde, and acetate unadjusted and adjusted for baseline will be estimated for treatment, nominal point, EIA days, and ALDH2 status. The Phoenix WinNonlin project file including all settings and analysis input file will be transferred to Dicerna when the biomarker PD analyses are completed.

The unadjusted and adjusted biomarker parameters will all be listed, and unadjusted parameters will be summarized by time point and treatment. Descriptive statistics (number, arithmetic mean, SD, CV%, geometric mean, gCV%, minimum, median, and maximum) will be presented by nominal points, treatment, ALDH2 status, and EIA days for absolute, and percentage change from the biomarker baseline, where appropriate. For time variables Tmin and Tmax, only median will be presented.

One way ANOVA model will be used to compare the unadjusted Biomarker parameters for DCR-AUD and Placebo for PP.

To visualize the comparison between treatment and placebo following alcohol consumption the following descriptive PD parameter graphs will be generated:

The mean (\pm SD) Cmax and AUC0-4h of acetaldehyde, acetate, and ethanol will be plotted with EIA days. Two mean Cmax figures will be prepared: one in μ M and another in ng/mL units.

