^a “Time 0” is immediately before the first sip of ethanol is consumed. All Time 0 assessments must be performed prior to initiation of alcohol intake.^b Participants will arrive at the site after a minimum 3-hour fast, then will be provided a standardized meal before receiving the first drink. Participants will be given 30 minutes to consume the meal.^c Catheter placement may be performed earlier in the day if preferred, but participants must be given at least a 20-minute rest period following placement of the venous access catheter prior to recording pre-dose vital signs and ECG. For EIAs conducted prior to a dosing day, the venous catheter will be left in place for PK sample collections.^d If multiple assessments are due at the same timepoint, the order of assessments should be ECG, vitals, blood draw, then any other assessments. The 60-minute symptom assessment should be conducted before the start of the 4th drink.^e To include pulse rate and blood pressure.^f Blood samples will be collected via venous access device. To include acetaldehyde, acetate, and ethanol.^g Participants will be questioned by site staff to assess the 6 symptoms (flushing, headache, lightheadedness, palpitations, nausea, and vomiting) associated with increased blood acetaldehyde levels.^h Ethanol will be consumed in 4 aliquots over an 80-minute period (20 minutes for each aliquot). Time windows do not apply to ethanol consumption. The ethanol will be mixed in a liquid that has no other alcohol, no caffeine, and is low in sugar. The dose of ethanol will be 0.8 g/kg (to a maximum of 56 g) for men and 0.68 g/kg (to a maximum of 48 g) for women. See protocol for ethanol administration stopping rules.

i AEs associated with administration of ethanol will include events spontaneously reported by participants beginning with the first sip of ethanol (symptoms elicited under direct questioning [footnote g] are not considered AEs).

Approved

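### Acetate AUC_Below in SAP Table 3-1 rests on an undefined baseline; on unadjusted profiles it is either about zero at any level of suppression or can be positive with no drug effect

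*SAP*

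**What the plan says.** SAP 3.2.5, Table 3-1, lists AUC_Below (WinNonlin name AUC_Below_B) for acetate only: "Area under the curve that is below the baseline (for acetate". The same table defines baseline once, for all baseline-dependent parameters, as the "Response value just prior to treatment administration". It does not say which treatment is meant.

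Two other baselines in the SAP could apply:

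- SAP 4.2.4, the general rule: "Baseline is defined as the last non-missing measurement prior to the date and time of the dose of study intervention".
- SAP 4.12.4, stated for the biomarker concentration listings: "The corresponding baseline for each timepoint will be taken on Day -1".

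Table 4-2 has no derivation row for AUC_Below. SAP 4.12.5 says only that "PD parameters will be calculated using drug effect model from the biomarker time data". SAP 4.12.1.2.1 sends the reader to Section 4.10 for the calculation method, and that section is marked not applicable.

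On direction, Protocol 1.1.1 states that "alcohol is first converted to acetaldehyde via alcohol dehydrogenase and then to acetic acid by ALDH2". Protocol 2.1 states that DCR-AUD should reduce ALDH2 and "thereby decrease the conversion of acetaldehyde to acetic acid after ethanol ingestion".

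**The concern.** Ethanol is a source of acetate, and the drug is meant to slow that conversion. Target engagement should therefore appear as a smaller rise in acetate after the drink. Nothing in the documents suggests a fall below the pre-drink level. An area below a pre-drink baseline looks for something that neither arm is expected to show.

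Acetate is one of three biomarkers under the second secondary objective. The single-dose study found no clear pattern of target engagement, and this study is meant to determine whether a PD effect can be observed. AUC_Below is the only parameter in Table 3-1 designed specifically for a reduction in acetate. A column of near-zero values under that name could be taken as evidence against acetate suppression.

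**Working it through.** The documents give no figure for this parameter, so there is none to reproduce.

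**Inputs from the documents.** The definitions above. Time 0 of the EIA "is immediately before the first sip of ethanol is consumed" (SAP Table 6-3, footnote a). The scheduled biomarker samples belong to the EIAs, so the last value before the first study dose is a late sample of the Day -1 EIA, after ethanol.

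**Assumed inputs.**
- Pre-ethanol acetate is 1 unit, with a peak of 1.5, 3 or 10 times that.
- 25% or 100% of the rise is still present at 240 min.
- The drug suppresses a fraction s of the rise, from 0 to 1.
- Sample CV is 0, 10 or 20%.
- Samples fall at 0 and every 30 min from 30 to 240 min (the time grid is broken in the extracted text).
- Areas use the linear trapezoid over 4 h.

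**Formulas, without noise.** The Day X curve is 1 + (1 − s) × rise(t). Let R be the area of the unsuppressed rise.

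- Time 0 baseline: the curve never goes below 1, so AUC_Below = 0 for every s.
- Time-matched Day -1 baseline: AUC_Below = s × R.
- SAP 4.2.4 baseline, when the rise is fully present at 240 min: AUC_Below = (peak rise × 4 h) − (1 − s) × R.
- Signed change in AUC0-4h from Day -1: −s × R.

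**Numbers for a 3-fold rise fully present at 240 min.** R = 7.10 unit·h and peak rise × 4 h = 2 × 4 = 8.00. At s = 0 the SAP 4.2.4 baseline gives 8.00 − 7.10 = 0.90. At other values of s it gives 0.90 plus the time-matched area.

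| Suppression | Time 0 baseline | SAP 4.2.4 baseline | Time-matched Day -1 | Change in AUC0-4h |
|---|---|---|---|---|
| 0% | 0 | 0.90 | 0 | 0 |
| 25% | 0 | 2.67 | 1.77 | −1.77 |
| 50% | 0 | 4.45 | 3.55 | −3.55 |
| 75% | 0 | 6.22 | 5.32 | −5.32 |
| 100% | 0 | 8.00 | 7.10 | −7.10 |

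Day -1 AUC0-4h is 4.00 + 7.10 = 11.10, so 50% suppression is a change of −3.55/11.10 = −32%, and full suppression −64%.

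**Sensitivity to the shape.** If 25% of the rise remains at 240 min, the SAP 4.2.4 reference is 1 + 0.25 × 2 = 1.5. The area then runs from 0.04 at no effect to 0.5 × 4 = 2.00 at full suppression. The acetate actually lost at full suppression is 5.60, against 7.10 in the sustained case. The parameter therefore falls from 8.00 to 2.00 while the true loss falls only from 7.10 to 5.60. It depends largely on how much acetate remained at 240 min on Day -1.

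**Range.** Across all assumed rises, the time 0 area stays at 0.00 without noise. The AUC0-4h change at full suppression runs from −1.4 (1.5-fold, 25% remaining) to −31.9 (10-fold, sustained).

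**With assay noise.**
- Time 0 baseline: at 10% CV the area is at most 0.09 up to 75% suppression and about 0.2 at 100%. At 20% CV it is at most 0.30 and about 0.4 to 0.5. A flat baseline AUC is 4.
- Time-matched baseline, 3-fold sustained rise, no drug effect: 0.51 at 10% CV and 1.04 at 20% CV, because only downward deviations count. The signed AUC0-4h difference in the same runs is −0.00 and −0.04.

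**The case against.** A reader might infer that AUC_Below is zero in both arms whatever DCR-AUD does. The documents do not support that as a general statement. It holds for a pre-ethanol baseline on unadjusted profiles. Under SAP 4.2.4 the area is not zero and it increases with suppression. SAP 4.12.5 also plans parameters on baseline-adjusted profiles. There the time 0 value is the difference between two pre-drink samples, near zero, so the area below it approximates the area between the Day -1 and Day X curves. That version would be informative. However, SAP 4.12.5 commits the adjusted parameters to listings, while the unadjusted ones go to the summary by treatment and the ANOVA.

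A reader might also infer that the acetate endpoint is lost. It is not. Table 3-1 names Cmax, tmax and AUC0-4h for acetate and lists Cav without restricting the analyte. Table 4-2 adds differences and percent changes from Day -1. These would show a blunted rise. The biomarker summary table and figures that the SAP describes name Cmax and AUC, not AUC_Below, so a table of zeros is possible but not explicitly planned.

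Importance is also limited. The primary objective is safety, the protocol calls its statistics descriptive, and the principal secondary endpoint is the symptom composite. All of this stands and limits the severity. It does not supply the missing baseline: no rule in the SAP tells an analyst which reference to use for AUC_Below.

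**Conclusion.** The concern holds in a narrow form, and its severity is minor. AUC_Below for acetate has an ambiguous baseline. On unadjusted profiles the pre-drink reading gives about zero at any suppression. The last-value-before-study-drug reading can give a positive area with no drug effect (0.90 or 0.04 unit·h in the two 3-fold examples) and varies with the Day -1 value at 240 min. As written it cannot be interpreted and could be misread as no acetate suppression. Other planned acetate measures can still detect suppression.

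The zero result needs only the direction of the pathway stated in the protocol and a pre-drink level that is otherwise stable over the EIA; noise adds a small positive amount. Every acetate magnitude here is illustrative, because the documents give no acetate levels, turnover or assay variability.

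**What to change.** 1. Delete AUC_Below_B for acetate from Table 3-1.
2. Name AUC0-4h(Day X) − AUC0-4h(Day -1), already defined in Table 4-2, as the acetate suppression measure. State that it is signed and that negative values mean suppression.
3. In SAP 4.12.5, summarise that difference by arm and EIA day instead of only listing it. Cover all post-dose EIAs: the change rows in Table 3-1 name days only to Day 57, while EIAs continue to Day 168.
4. If AUC_Below is kept, compute it against the participant's time-matched Day -1 curve and note that it has a positive noise floor under no effect.
5. State that AUC_Above and Cmax_Above for acetaldehyde use the time 0 sample of the same EIA as baseline.

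The cost is SAP wording and one summary output. All samples are already scheduled. After SAP finalisation, the change would go through the method modification form named in SAP Section 1.
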